### 6.12.2 Primary Efficacy Analysis

	Sponsor:	Sensorion
	Protocol Number:	SENS 401-201
STATISTICAL ANALYSIS PLAN. PHASE 2-3-4		

The null and alternative hypotheses for part 1 of the study are as follows, where  $\mu_H$ ,  $\mu_L$  and  $\mu_P$  are defined as the mean change in PTA of the high dose, low dose, and placebo respectively:

$H_{0H}: \mu_H - \mu_P = 0$ ,  $H_{AH}: \mu_H - \mu_P < 0$  (greater decrease on high dose)

$H_{0L}: \mu_L - \mu_P = 0$ ,  $H_{AL}: \mu_L - \mu_P < 0$  (greater decrease on low dose)

### **Analysis of Part 1**

To preserve type I error rate during part 1, the above hypotheses will be tested according to a fixed-sequence testing strategy: the comparison of the high dose versus placebo will be tested first at 5% one-sided significance level; then the comparison of the low dose versus placebo will be tested at 5% one-sided significance level conditionally to the significance of the high dose. This procedure is compliant with the principle of the closed test procedure (Marcus et al., 1976, Koch 1996). In the event that the null hypothesis  $H_{0H}$  cannot be rejected for the high dose, the p-value associated with  $H_{0L}$  will still be provided but considered exploratory. The comparison of the high dose versus the low dose will be considered exploratory.

### **Analysis of Part 2**

After completion of Part 1, one dose will be dropped and the other will be carried over to part 2. Hence at the end of part 2 only one null hypothesis will be tested:

$H_0: \mu_T - \mu_P = 0$ ,  $H_A: \mu_T - \mu_P \neq 0$

Where  $\mu_T$  is the change from baseline in PTA for the active treatment arm of part 2. This hypothesis will be tested at the 5% two-sided significance level.

### **Analysis details**

Descriptive statistics (n, mean, SD, median, Q1, Q3, min, max) of observed data by visit (Day 7, 14, 28) and treatment group (placebo, SENS401 29 mg, SENS401 43.5 mg) displaying baseline, post-baseline, change will be provided.

Mean changes from baseline of the hearing loss at days 7, 14, and 28 will be analyzed using a restricted maximum likelihood (REML)-based repeated measures approach under the assumption of data missing at random (MAR). Analyses will include the categorical, fixed covariates of site category (non-ancillary, ancillary), duration of disease ( $\geq 24$  hours or  $< 24$  hours), and oral

	Sponsor:	Sensorion
	Protocol Number:	SENS 401-201
STATISTICAL ANALYSIS PLAN. PHASE 2-3-4		

corticosteroids intake at baseline (yes or no) as entered in the IWRS and the fixed, categorical effects of treatment, visit (Day 7, Day 14, Day 28), and treatment-by-visit interaction, as well as the continuous, fixed covariates of baseline score and baseline score-by-visit interaction. An unstructured (UN) covariance structure will be used to model the within-patient errors. If this analysis fails to converge, simpler structures such as first-order ante-dependent ANTE(1), first-order autoregressive AR(1), or compound symmetry (CS) will be tested in a model without treatment effect. The covariance structure converging to the best fit, that is, with the lowest Akaike's information criterion (AIC), will be used in the full model. The Kenward-Roger approximation will be used to estimate denominator degrees of freedom. The estimations and standard errors of the contrasts of interest will be derived from this model. For each timepoint the marginal predicted means (Least Squares Means) and corresponding standard error and confidence interval (consistent with the significance level applied for the study part considered) will be displayed (and also graphically illustrated with mean changes on y-axis and time on the x-axis by treatment groups). The p-value of the visit by treatment interaction will be provided. For each timepoint, one-sided p-values for the comparisons with Placebo and for the comparison of high dose versus low dose will also be displayed with comparisons with Placebo at Day 28 being the comparisons of primary interest while the other comparisons are secondary.

SAS code to perform the analysis described above for part 1 (i.e. when 3 treatment arms are available) is provided below wherein TRT01PN is the treatment group, AVISITN is the analysis visit (Day 7, 14, and 28) as defined in Section 6.2.15, ANCIL is the site category (non-ancillary, ancillary), DHR is the duration of the hearing loss ( $\geq 24$  hours or  $< 24$  hours) strata, and CORT is the intake of oral corticosteroids at baseline (Yes, No) strata. Note that the ordering of the coefficients for the ESTIMATE statements may need to be updated depending on the entry order in the CLASS statement and will be different for the analysis of part 2 (where only 2 treatment arms will be present). Moreover, 'TYPE=UN' may need to be replaced with 'TYPE=ANTE(1)', 'TYPE = AR(1), or 'TYPE=CS' if the model with 'TYPE=UN' failed to converge.

```
proc mixed data = <dataset>;
  class subjid trt01pn avisitn ANCIL DHR CORT;
  model chg = trt01pn avisitn trt01pn*avisitn base base*avisitn ANCIL DHR
  CORT / ddfm = kr;
  repeated avisitn / type = un subject=subjid(trt01pn);
  lsmeans trt01pn*avisitn / cl e alpha = 0.10;
  estimate 'High vs Placebo, day 28'
    trt01pn -1 0 1
    trt01pn*avisitn 0 0 -1 0 0 0 0 0 1 / alpha = 0.10 cl;
  estimate 'Low vs Placebo, day 28'
```

	Sponsor:	Sensorion
	Protocol Number:	SENS 401-201
STATISTICAL ANALYSIS PLAN. PHASE 2-3-4		

```

trt01pn -1 1 0
trt01pn*avisitn 0 0 -1 0 0 1 0 0 0 / alpha = 0.10 cl;
estimate 'Low vs High, day 28'
trt01pn 0 1 -1
trt01pn*avisitn 0 0 0 0 0 1 0 0 -1 / alpha = 0.10 cl;
run;

```

A similar code (with 2 groups only and alpha = 0.05, two-sided p-value) will be used for the analysis of Part 2.

The number of subjects, the affected ear and the type of reference (unaffected contralateral ear, reference values from a pre-existing audiogram, ISO 2017) will be tabulated by treatment group, stratification groups, and overall.

All PTA data will also be listed.

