## 9.10 Concomitant treatment

### 9.10.1 Background therapy

Corticosteroids by oral route (including but not limited to prednisone, methyl prednisolone, dexamethasone) are usually considered as the standard of care (Appendix 6). The guidelines published by the AAO-HNS recommend prednisone for patients with SSNHL within 2 weeks after the diagnosis, with a recommended dose of Prednisone 1 mg/kg/day (max: 60 mg/day), or Methylprednisolone 48 mg/d or Dexamethasone 10 mg/d given as a single dose for 7-14 days, then taper over similar time period. Since there is no harmonization on this clinical practice,

---

each site will be requested to pre-specify the type and dosage regimen of oral corticosteroid that will be given to patients as standard of care. Unless contra-indicated, the pre-specified oral corticosteroids will be prescribed to all patients at a given site. The time, dose and route of administration will be recorded on the e-CRF. The randomisation will be stratified according to the corticosteroid intake. Compliance of the corticosteroids intake will be assessed by the investigator at every on-site visit from the patient diary. Any contra-indication will be recorded on the e-CRF at the sites.

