### 6.7.2 Disease Characteristics and Other Relevant Baseline Data

The following variables will be summarized:

- Duration of current hearing loss episode at time of randomisation (in hours): randomisation date/time-SSNHL onset date/time, continuous and by class (<24 hours, [24; 48[, [48; 72[, >72 hours)
- Cause of current hearing loss/SSNHL: idiopathic, trauma (including noise induced), infectious, otologic disease, ototoxic drug intake, vascular/hematologic, neoplastic
- Oral Corticosteroids (CM.CMCAT = “ORAL STEROID”) for SSNHL (CM.CMINDC = “SSNHL”) at baseline (ongoing or started the day of first study treatment intake): yes/no and type (prednisone/prednisolone, methylprednisolone, dexamethasone or other)
- Otologic history: ear used for telephone and recent switch, professional exposure to very loud noise, recreational exposure to very loud noise, history of severe ear problems (previous SSNHL, frequent otitis media, past history of ear surgery, wearing hearing aids, past history of tinnitus in each ear), ear/head/neck/nose/throat problems (infection, respiratory tract infection, ear pain, ear pressure, otorhea, severe headache or migraine, recent head or neck trauma, recent baro trauma, exposure to loud noise, past otologic evaluation)

	Sponsor:	Sensorion
	Protocol Number:	SENS 401-201
STATISTICAL ANALYSIS PLAN. PHASE 2-3-4		

- Baseline Pure Tone Audiometry air conduction average of the hearing threshold of 3 contiguous most affected hearing frequencies in decibels as identified at study entry (PTA) for the current hearing loss episode:
  - Initial frequency range ( $\leq 2000$  Hz,  $> 2000$  Hz) derived as the mean between the lowest and the highest of the most affected frequencies
  - Affected ear side (right, left)
  - Affected ear PTA continuous (in decibels)
  - Affected ear PTA by class ( $<20$  dB,  $\geq 20$  dB to  $\leq 35$  dB,  $>35$  dB to  $\leq 50$ dB,  $>50$  to  $\leq 70$  dB,  $>70$  to  $\leq 90$  dB,  $>90$  dB)
  - Reference type (contralateral ear, previous PTA, reference frequency)
  - Reference PTA continuous
  - Reference PTA by class
  - Hearing loss (difference between the PTA on affected ear and the reference PTA for the identified frequencies) continuous (in decibels)
  - Hearing loss by class according to American Speech-Language-Hearing Association criteria (ASHA) ( $<16$ , 16 to  $<26$ dB, 26 to  $<41$ dB, 41 to  $<56$ dB, 56 to  $<71$ dB, 71 to  $<91$ dB,  $\geq 91$ dB)

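### The primary model's per-arm LS means weight the strata equally, so the reported Day 28 means and CIs describe a half-without-steroids population rather than the trial's own; the dose-versus-placebo tests are unaffected

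*SAP*

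**What the plan says.** SAP 6.12.2 (Analysis details) declares the three stratification factors as classification variables, "class subjid trt01pn avisitn ANCIL DHR CORT", and fits them as additive main effects: "model chg = trt01pn avisitn trt01pn*avisitn base base*avisitn ANCIL DHR", with CORT on the next line. There is no treatment-by-stratum term.

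The arm means come from "lsmeans trt01pn*avisitn / cl e alpha = 0.10". The options print limits and coefficients and set the level; none sets the weights, and no SAP text does so either. The SAP says what will be shown: "For each timepoint the marginal predicted means (Least Squares Means) and corresponding standard error and confidence interval", tabulated and plotted by arm.

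The primary comparison comes from a separate ESTIMATE statement whose interaction row is "trt01pn*avisitn 0 0 -1 0 0 0 0 0 1 / alpha = 0.10 cl". It carries no coefficient on any stratum factor.

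On steroids, Protocol 9.10.1 states: "Unless contra-indicated, the pre-specified oral corticosteroids will be prescribed to all patients at a given site". The model uses "corticosteroids intake at baseline (yes or no) as entered in the IWRS". For the baseline table, SAP 6.7.2 counts steroid use "at baseline (ongoing or started the day of first study treatment intake" as yes.

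**The concern.** Without an observed-margins request, PROC MIXED builds each LS mean with weight one half on each level of every classification factor outside the LS-mean effect. Each arm's mean is thus the prediction for patients who are half on steroids and half not, half under 24 hours from onset, and half from ancillary sites. The steroid split cannot be expected to look like that in a trial that prescribes steroids to everyone who can take them. The label marginal suggests the trial's own population.

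Two things follow. If steroid intake is related to PTA change, every arm mean moves by the same amount. Even if it is not, the poorly estimated coefficient of a small stratum enters each arm's SE with a weight of up to nearly one half.

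What is at stake is how readers judge recovery on placebo and on each dose. Protocol 5.1 cites spontaneous recovery of up to 32–65%, so the absolute level in each arm will attract attention.

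**Working it through.** **Inputs.** SD 30 dB, correlation 0.45 between Day 28 and baseline, difference 15 dB, 37 per arm, 111 in total (SAP section 4). Adjusted SD = 30 × √(1 − 0.45²) = 26.79 dB, the figure used in SAP section 7. The share p of patients without steroids and the steroid coefficient β are not in the documents, so ranges are shown.

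**Plan's own figure.** n per arm = 2 × (1.645 + 0.674)² × (26.79/15)² = 34.3 by the normal formula. The t-based calculation gives 35, matching the fixed-design size in SAP section 4. The SD input is therefore the one the plan used.

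**Shift in an arm mean.** Equal-weight minus observed-margin mean = (0.5 − p) × β for the steroid factor. With β = 10 dB (assumed):
- p = 5%: 0.45 × 10 = 4.5 dB
- p = 10%: 0.40 × 10 = 4.0 dB
- p = 20%: 0.30 × 10 = 3.0 dB

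**SE of an arm mean.** With observed margins it is about 26.79/√37 = 4.40 dB. With equal weights, and the no-steroid patients spread evenly over the arms,

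SE² = 26.79² × [1/37 + k × (0.5 − p)² / (111 × p × (1 − p))].

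The ratio of the two SEs is √(1 + kA), with A = (0.5 − p)² / (3p(1 − p)).

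The factor k is the variance of the steroid coefficient relative to estimating it from Day 28 alone. The planned model has no stratum-by-visit term, so the coefficient is estimated from Days 7, 14 and 28 together and k is below 1. The within-patient correlation is assumed to be 0.5–0.9, with visit SDs either equal or rising as 0.7, 0.85 and 1 of the Day 28 value.
- Equal SDs, correlation 0.9: k = (1 + 2 × 0.9)/3 = 0.933, the largest value.
- Rising SDs, correlation 0.9: k = 0.404, the smallest value checked.

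| Without steroids | A | SE increase, k = 0.404 | SE increase, k = 0.933 | Day 28 only, k = 1 |
|---|---|---|---|---|
| 5% | 1.421 | 25% | 53% | 56% |
| 10% | 0.593 | 11% | 25% | 26% |
| 20% | 0.188 | 4% | 8% | 9% |
| 30% | 0.063 | 1% | 3% | 3% |

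The repeated-measures information matrix over the same assumptions gives about 26–53%, 12–25% and 4–8% at 5%, 10% and 20%, and 3% or less at 30%. The closed form agrees to within about one point. At 10%, the 90% CI half-width goes from 1.645 × 4.40 = 7.2 dB to between 8.1 dB (1.645 × 4.90) and 9.0 dB (1.645 × 5.49).

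**Treatment difference.** Subtracting two arm means at the same visit cancels every stratum weight, whether 0.5 or p. The coefficients that remain are those in the ESTIMATE statement. The SE of the difference is about 6.25 dB under both weightings; the simple check is 26.79 × √(2/37) = 6.23 dB.

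**The case against.** The strongest reply is that nothing confirmatory depends on these means. The hypotheses concern differences, and those are identical under either weighting. That stands.

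Three further replies also stand:
- An equal-weight LS mean and its CI are valid for the equal-weight population. The question is which population the report should describe, so the intervals are not wrong in themselves.
- Readers have other help. Observed means and SDs by arm and visit are planned, the strata distribution is tabulated (SAP 6.6), and the E option prints the coefficients.
- The no-steroid level is the IWRS entry at baseline, so it may include patients who start steroids later. The wider definition in SAP 6.7.2 serves a baseline table. A minority level is the natural expectation, but its size is unknown, and at 30% almost nothing is lost. Protocol 13.5.1 also allows a blinded review to drop a covariate.

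A reader might infer more than the documents support:
- That all three factors are badly unbalanced, with correspondingly larger inflation. No shares are given for under 24 hours or for ancillary sites, and nothing in the documents implies that either is rare.
- That the SE inflation is 56%, 26% and 9%. Those values come from a Day-28-only model, which is not the planned one.
- That the copy-reference ANCOVA in SAP 6.12.3 has the same defect in its results. Its pooling step reads only the differences.

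None of this explains why the SAP should present as marginal a set of means standardised to a half-without-steroids population.

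**Conclusion.** The point holds as a reporting improvement. The per-arm Day 28 LS means, SEs, CIs and plot answer for a population the trial is not designed to enrol. If 5% to 20% of patients are without steroids, the SE inflation runs from about 26–53% down to 4–8%, and each 10 dB of steroid coefficient shifts every arm mean by 4.5 down to 3.0 dB. These sizes assume complete data, 37 per arm, a residual SD of 26.79 dB, the other two factors balanced, and the correlations and visit SDs stated in the working. The shift is zero if the factor is balanced or unrelated to the outcome. The SE inflation needs only imbalance.

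It would be wrong to read this as an error in the efficacy test. With no treatment-by-stratum interaction, the dose-versus-placebo estimates, CIs and p-values are the same either way.

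**What to change.** Request observed margins in the primary model's LSMEANS statement, for example `lsmeans trt01pn*avisitn / om=margins cl e alpha=0.10;`. The margins data set should hold every ITT patient at every modelled visit (Days 7, 14 and 28) with all model variables: treatment, visit, baseline, ANCIL, DHR and CORT. Each patient then counts equally whatever visits were attended, and the data set matches the visit terms in the model. Add one SAP sentence saying that LS means are standardised to the ITT strata distribution.

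Do the same in the secondary-endpoint repeated-measures models, adding Day 84 rows where that visit is modelled, and in the Part 2 code. Leave the ESTIMATE statements as they are. The copy-reference ANCOVA needs no change.

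The cost is one option, a small data set, one sentence and a test run on dummy data. No hypothesis test changes. If equal weights are preferred, the SAP should say so and not call the means marginal.

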### 6.12.3 Sensitivity Analyses

A first sensitivity analysis will assess the impact of major protocol violations to study results, by repeating the primary analysis on the Per Protocol population.

A second sensitivity analysis will further assess the impact of the MAR assumption of the main analysis by imputing missing data at Day 7, Day 14 or Day 28 under control-based multiple imputation framework under the assumption that data are missing not at random (MNAR) and using the Copy Reference (CR) approach (Carpenter 2013). Thus, instead of imputing a single value for each missing observation, a set of values will be generated from the model resulting in as many distinct complete datasets without missing data. The imputation model will include the PTA baseline, the three stratification factors (site category, hearing loss duration and intake of corticosteroids at baseline) and the Day 7, Day 14, Day 28 PTA data. Missing data at Day 7, Day 14, and Day 28 for subjects from all three treatment groups will be imputed using data observed in the placebo group. This approach assumes that patients with missing data in the active treatment groups have outcomes trending towards outcomes observed in the placebo group, i.e., the imputations result in a treatment effect that gradually diminishes towards the placebo group. In a first step "intermittent" missing data (a post-baseline is missing but one or more later assessments are available) will be first imputed by a Markov Chain Monte-Carlo (MCMC) method using a non-informative Jeffrey's prior, thus creating multiple partially imputed "monotone" datasets; then, the remaining missing data will be imputed once in each of the "monotone" imputed datasets using the CR approach leading finally to multiple complete imputed datasets. An analysis of covariance (ANCOVA) will then be used to analyze the change from baseline to Day 28 on each complete

		Sponsor:	Sensorion
		Protocol Number:	SENS 401-201
STATISTICAL ANALYSIS PLAN. PHASE 2-3-4			

imputed dataset. The following terms will be included in the ANCOVA model: the PTA baseline, the three stratification factors (site category, hearing loss duration and intake of corticosteroids at baseline), and the treatment group. Uncertainty in the imputations will be reflected appropriately in the analysis by combining the results on each imputed dataset using Rubin's methodology.

More specifically, the imputations will be performed in two steps: “intermittent” missing data (a result is missing but one or more results are available at following visits) will be first imputed by a MCMC method using a non-informative Jeffrey’s prior, thus creating 500 partially imputed “monotone” datasets; then, the remaining missing data will be imputed once in each of these 500 “monotone” imputed datasets using the CR approach leading finally to 500 complete imputed datasets.

The two-step MI procedure will be implemented by the following SAS code:

```
proc mi data=<dataset> nimpute=500 seed=32767 min = . . . . -10 -10 -10
max = . . . . . 120 120 120 minmaxiter = 1000000 out=h2;
  where base ne .;
  mcmc impute = monotone;
  var trt01pn ANCIL DHR CORT base Day07 Day14 Day28;
run;

proc mi data=h2 nimpute=1 seed=32767 min = . . . . . -10 -10 -10 max = . . . .
. . 120 120 120 minmaxiter = 1000000 out=h3;
  by _imputation_;
  class trt01pn ANCIL DHR CORT;
  var ANCIL DHR CORT base Day07 Day14 Day28;
  mmar model (Day07 Day14 Day28 / modelobs=(trt01pn = "1"));*"1" = placebo;
  monotone regression;
run;

data h3;
  set h2;
  chg = Day28 - baseline;
run;
```

An analysis of covariance (ANCOVA) model will then be used to analyze this endpoint on each imputed dataset using the following SAS code for Part 1:

```
proc mixed data=h3;
by _imputation_;
  class trt01pn ANCIL DHR CORT;
  model chg = ANCIL DHR CORT base trt01pn / solution;
  lsmeans trt01pn / diff=control("3") cl;*"1" = placebo;
  ods output lsmeans =lsm diffs=lsmdiffs ;
run;
```

	Sponsor:	Sensorion
	Protocol Number:	SENS 401-201
STATISTICAL ANALYSIS PLAN. PHASE 2-3-4		

Uncertainty in the imputations will be reflected appropriately in the analysis by combining the results on each imputed dataset using Rubin’s methodology (Rubin 1987). The final estimate is the mean of the estimates from the 500 imputed datasets, and the final variance is the sum of the average within-imputation variance and (1 + 1 / 500) times the between-imputation variance. From the final point estimate and variance, the 90% CI will be determined. The results aggregation of the MI procedure after analysis of the 500 imputed datasets will be implemented by the following SAS code:

```
proc mianalyze data=lsmdiffs alpha=0.10;
  by trt01pn;
  modeleffects Estimate;
  stderr StdErr ;
run;

proc mianalyze data=lsmdiffs alpha=0.10;
  modeleffects Estimate;
  stderr StdErr ;
run;
```

A similar code (with 2 groups only and alpha = 0.05) will be used for the analysis of part 2

A third sensitivity analysis will assess the impact of the use of rescue therapy by repeating the primary analysis after having set to missing all PTA assessments performed after initiation of a rescue therapy and then imputing each missing Day 28 of a subject having received rescue therapy by the subject baseline.

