The first GST look was performed, and the outcome was a recommendation to continue Part 1 in the absence of crossing of any boundary. The second GST look was not performed because all amendment protocol approvals were not obtained yet at time when the sample size of the second GST was reached. The final look will finally not be performed as it does not have enough added value compared to the analysis planned in the DMC SAP section 2.6.

**Part 2:** A sample size of 190 patients (95 patients per treatment arm) was retained corresponding to following assumptions:

- Comparison to placebo performed at 5% two-sided significance level
- Power of the comparison to placebo set to 90%
- Randomization ratio 1:1
- Intra-group standard deviation of 20 dB is estimated based on recent publication in SSNHL with other pharmaceutical therapies
- A difference to placebo of 10 dB is expected as considered clinically meaningful
- 10% dropout rate

The sample size of Part 2 was not revised at time of the amendment for protocol version 4.0 but will be re-estimated based on Part 1 results when available. The final sample size will be submitted for approval to competent authorities prior to the pivotal part start.

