## 10 LIST OF TABLES, FIGURES AND LISTINGS

The following table includes details of the tables, figures and listings to be included within each section of the eCTD. The eCTD section is shown in bold. The following validation methods maybe used:

- Independent programming of numbers and manual review of format (IP)
- Independent programming by statistician of numbers and manual review of format (Stat IP)
- Manual review (MR)
- Code review (CR)

Furthermore, separate set of outputs will be produced for the Part 1 and Part 2 of the study:

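### The SAS code given for the Copy Reference sensitivity analysis discards the Copy Reference imputations and contradicts the SAP's own description

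*SAP*

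**What the plan says.** Section 6.12.3 of the SAP plans three sensitivity analyses of the primary endpoint. The second tests the missing-at-random assumption behind the primary repeated-measures model. Its prose is clear. Intermittent gaps are filled first by MCMC. Remaining gaps for "subjects from all three treatment groups will be imputed using data observed in the placebo group". Each monotone dataset is completed once, "using the CR approach leading finally to 500 complete imputed datasets". Each is then analysed by ANCOVA on the Day 28 change and the results are combined by Rubin's rules.

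The code is not offered as an illustration: "The two-step MI procedure will be implemented by the following SAS code". In outline:

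- Step 1 is PROC MI with monotone MCMC. The variables end with Day 7, Day 14, Day 28, and the output is `h2`.
- Step 2 is PROC MI with the placebo-based model, where placebo is `trt01pn` level 1. The output is `h3`.
- A data step named `h3` reads `h2` and computes "chg = Day28 - baseline".
- The ANCOVA on `h3` requests "lsmeans trt01pn / diff=control('3') cl;*'1' = placebo".
- There are two PROC MIANALYZE calls, one BY treatment and one without BY.

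For Part 2 the section adds: "A similar code (with 2 groups only and alpha = 0.05) will be used for the analysis of part 2". Tables 14.2.1.3a and 14.2.1.3b carry the result, under a title announcing MNAR Copy Reference imputation.

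**The concern.** The code named as the implementation does not carry out the analysis described beside it, and the SAP does not say which governs when the two differ. Nothing else in the plan does this job: the per-protocol repeat addresses protocol deviations, and the third analysis addresses rescue therapy. If the listing is followed and happens to run, the table would present a complete-case estimate under an MNAR title. It would show no penalty for dropout and would appear to support the primary result. Choosing between prose and code after unblinding is what pre-specification is meant to prevent.

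**Working it through.** **1. Does the code deliver 500 complete datasets?** The prose calls a gap intermittent only if a later visit has a result. Day 28 is the last visit in the variable list, so a missing Day 28 can never be intermittent, and monotone MCMC leaves it missing in `h2`. Step 2 fills it in `h3`. The data step then rebuilds `h3` from `h2`, so the step 2 values are lost before PROC MIXED reads the dataset. The SAP's figure of 500 complete datasets is not reproduced.

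**2. What does the ANCOVA then estimate?** Its terms are the Day 28 change, baseline, three strata and treatment. Day 7 and Day 14 do not enter, so the MCMC values cannot affect it. All 500 fits are the same Day 28 complete-case ANCOVA, with between-imputation variance 0. This assumes `baseline` exists in the dataset. Every other statement uses `base`; if `baseline` is absent, the change is missing for everyone and nothing is estimated. On either branch no placebo-based value reaches the result.

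**3. Placebo level.** No single coding makes the listing right.

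| Coding of `trt01pn` | Imputation reference (level 1) | Contrast control (level 3) |
|---|---|---|
| Placebo first (ESTIMATE statements in 6.12.2; both code comments) | Placebo: correct | High dose: gives placebo minus high (sign reversed) and low minus high; low versus placebo is not produced |
| Placebo third (label order in 6.3) | An active arm: wrong | Placebo: correct |

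**4. Size of the lost attenuation.** Let D be the true Day 28 effect, d the fraction missing Day 28, f the ratio of the effect at the last observed visit (taken as Day 7) to the Day 28 effect, and b the slope of Day 28 on Day 7.

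- Copy Reference estimate = (1 − d)·D + d·b·f·D
- Lost attenuation = d·D·(1 − b·f)

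Inputs from SAP section 4: D = 15 dB (Part 1), D = 10 dB (Part 2), and "10% dropout rate", which is stated for Part 2 only. Assumed: f from 0 to 1, b from 0.5 to 0.9, and a second missing rate of 20%. The product b·f then runs from 0 to 0.9; the central case is 0.5 × 0.7 = 0.35.

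| | b·f = 0.9 | b·f = 0.35 | b·f = 0 |
|---|---|---|---|
| Part 1, d = 0.10 | 0.1 × 15 × 0.10 = 0.15 | 0.1 × 15 × 0.65 = 0.98 | 0.1 × 15 = 1.5 |
| Part 1, d = 0.20 | 0.30 | 1.95 | 3.0 |
| Part 2, d = 0.10 | 0.10 | 0.65 | 1.0 |

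**5. Simulation check.** Settings: 37 per arm, SD 30 dB and baseline–Day 28 correlation 0.45 (SAP section 4), true high-dose effect −15 dB. Assumed: the other visit correlations, and dropout at random spread over the visits. The control level was set to placebo so that the two analyses can be compared. Mean high-minus-placebo over 400 trials:

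| Missing Day 28 | Code as printed (mean n) | Copy Reference (n = 111) |
|---|---|---|
| 5% | −15.2 dB (about 106) | −14.6 dB |
| 10% | −15.4 dB (about 100) | −14.2 dB |
| 20% | −15.5 dB (about 89) | −13.3 dB |

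The between-imputation variance of the printed code was 0 to rounding. Under Copy Reference it was 1.1, 3.1 and 8.3 in single simulated trials at the three rates. The gap of about 1.2 dB at 10% lies inside the range from the formula.

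**6. The MIANALYZE call without BY (Part 1).** The adjusted SD is 30·√(1 − 0.45²) = 26.79, so the SE per contrast is 26.79·√(2/37) = 6.23. Suppose the true effects are 15 dB (high) and an assumed 7.5 dB (low). The call averages 500 copies of each contrast: estimate (15 + 7.5)/2 = 11.25; between variance 3.75² × 1000/999 = 14.08; SE = √(6.23² + 1.001 × 14.08) = 7.27. That figure estimates neither comparison.

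**The case against.** The strongest reply is that the method is already pre-specified in prose: reference arm, both steps, number of imputations, ANCOVA terms and pooling formula. The output tables are assigned independent programming by a statistician, and a between-imputation variance of exactly zero would be conspicuous. As printed, the block may well stop with an error at `baseline`, so a misleading table needs part of the listing to be repaired and the rest left alone. All this is fair and limits the harm. It does not remove the conflict, and the safeguard works only if the second programmer uses the prose and not the code the SAP names.

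A second reply is that two of the faults each turn on a single digit (`h2` for `h3`, level 3 for level 1), which could be a fault in reading the PDF. That cannot be excluded, but nothing shows it, and it does not explain `baseline` or the pooling call without BY. Other oddities in the block, such as the keyword for the MNAR statement and the lengths of the MIN and MAX lists, could be reading faults and are not relied on here.

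Third, the effect is small and rests on assumptions. No missing rate is given for Part 1. Protocol section 11.3.1 asks for end-of-treatment assessments at early discontinuation, and SAP section 6.2.16 accepts Days 20 to 36 as Day 28, so fewer values may be missing than patients drop out. At 10% missing, the largest Part 1 loss (1.5 dB) is about a quarter of the 6.23 dB standard error. This stands. The pooling call without BY is also a lesser point: it would suit two arms, and no table announces a pooled two-dose figure.

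**Conclusion.** The concern holds. The listing contradicts the prose, and the Copy Reference imputations never reach the analysis, whatever the dropout rate and whichever way treatment is coded. The consequence is conditional: a complete-case result under an MNAR title if `baseline` exists, no result if it does not. At 10% missing Day 28, the attenuation that should appear and would not is 0.15 to 1.5 dB of 15 dB in Part 1 (central case about 1.0 dB) and 0.1 to 1.0 dB of 10 dB in Part 2. At an assumed 20%, the Part 1 range is 0.3 to 3.0 dB. These figures rest on the assumed f and b, and on applying the Part 2 dropout figure to Part 1. The primary model, the alpha and the sample size are not touched. This should be fixed because it is the plan's only check of the missing-at-random assumption.

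**What to change.** Make the code match the prose in section 6.12.3:

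- Derive the change from the step 2 output and the existing variable name: `data h3; set h3; chg = Day28 - base; run;`.
- State the `trt01pn` coding once, and use the same placebo level in the imputation reference and the ANCOVA control. Under the coding implied by 6.12.2 and the code comments, that is level 1 in both places.
- For Part 1, sort `lsmdiffs` by `trt01pn` (it leaves the ANCOVA ordered by imputation), keep the MIANALYZE call with BY, and delete the one without.
- Carry the same corrections to the Part 2 version and recheck the control level there, since with two arms level 3 may not exist.
- Check the whole block against the signed SAP file, and say that the prose governs if the two still differ.

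The cost is a few lines of SAP code. Data collection, sample size and the primary analysis do not change.
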